
changes (constant controls and therapies, sudden change in the style of life, drug therapies and its effects, physical modifications), and that this can favor a mental reorganization of negative events, a greater expression and regulation of the emotions related to them, and the improvement of the relational style with family members and medical staff. Furthermore, this could be associated with a greater ability to cope with the consequences and psychophysical changes following transplantation and encourage greater levels of adherence with effects on the risk of organ rejection and health costs.

The hypothesis of the present study was that the expressive writing treatment produces an improvement in the emotional condition, levels of adherence and renal function, and a decrease in healthcare spending.

Material and Method

Thirty-five patients were recruited at the kidney transplant center of the Policlinico Umberto I, Sapienza University of Rome. Each participant completed an informed consent form. The sample was divided into two groups in a randomized way. Of the 35 patients, 3 were excluded for not completing the task, due to logistical problems and due to the hospital situation, 1 refused to perform the writing task, and finally 3 dropped to T2 (3rd post-transplant month). Of the remaining 28 recruited patients, 2 had an acute rejection before starting the writing task. The final sample is $n = 26$.

Each participant completed an informed consent form. Adult patients of Italian nationality with a sufficient level of education in order to understand the questionnaires and to execute the writing task were included in the study. Patients with uncompensated psychopathology, already excluded in the pre-transplant psychiatric evaluation, and / or affected by cognitive impairment, were excluded.

The study had 3 phases:

Pre-operative phase (T0)

The time of admission, just before the kidney transplant. In this phase to all participants were asked socio-demographic information and specific characteristics of the pathology in progress (eg. duration of dialysis treatment, date of transplantation, onset of disease). Then, they completed the following self-administered questionnaires: Beck Depression Inventory (BDI) for the evaluation of depression (Beck et al., 1961), State Trait Anxiety Inventory I and II (STAI Y1 - STAI Y2) for the evaluation of trait and state anxiety (Spielberger

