et al. , 1983), Toronto Alexythymia Scale 20-item (TAS-20) (Bagby et al., 1994) for assessing the ability to identify and describe one's emotions, Interpersonal Reactivity index (IRI) (Davis et al, 1980) for the evaluation of empathy and the Health Locus of Control (HLC) for the evaluation of the patient's beliefs on his state of health and a questionnaire for the evaluation of healthcare costs, built ad hoc. To assess the level of adherence, each patient answered to the following question: "Have you ever forgotten to take the drugs prescribed by your treatment plan?" with dichotomous answer yes / no. Finally, in order to assess the pre-transplant renal function values, such as Creatinine, CDK-EPI and azotemia, were collected.

Writing Phase (WP)

Five days after the operation, patients belonging to the experimental group, performed the writing task related to their deepest emotions, thoughts and concerns focused on the disease and the transplant itself, for 3 consecutive days, for 20 minutes a day. They did the writing session in a closed, silent room, which guaranteed their privacy. The instructions were according to the standard delivery by Pennebaker, creator of the technique (Pennebaker et al., 1986), translated and adapted for the specific hospital situation already proposed in a study on urological patients by Solano et al, 2007. Instead, the control group performed the neutral writing task, related to the description of an object in their room, without mentioning emotions, but just describing in a neutral way what they saw, for 3 consecutive days, 20 minutes each day.

The *day of discharge Phase (T1)* and *three months follow up (T2)* all participants filled the questionnaire completed before the operation and they had the blood analysis according to the hospital protocol for transplanted patients.

Statistical analysis

Statistical analysis will carry out using the software Statistica Soft 10.0. In order to evaluate the effectiveness of the expressive writing intervention, an analysis of variance with repeated measures (Fisher's F) and planned comparisons between the two randomized groups will be performed on psychological variables, the renal function indices and the health expenditure. The times taken into consideration will be T0, T1, T2 and the differences between T0, T1 and T2 will be respectively evaluated. To test the hypotheses on the dichotomous variable of adherence, Chi Square test will carry out.

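### The three-time repeated-measures F has no sphericity handling: the group-by-time test can run at up to 8.7% for an assumed 5%, and planned comparisons are exposed if their error term is pooled

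*Combined protocol and SAP*

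**What the plan says.** For the continuous outcomes, the Statistical analysis section plans "an analysis of variance with repeated measures", tested with Fisher's F, and says that "planned comparisons between the two randomized groups will be performed on psychological variables, the renal function indices and the health expenditure". On timing it says "The times taken into consideration will be T0, T1, T2" and that "the differences between T0, T1 and T2 will be respectively evaluated".

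Material and Method defines T0 as "The time of admission, just before the kidney transplant". T1 is the day of discharge and T2 is three months after transplant. The same section says "The sample was divided into two groups in a randomized way" and gives a final sample of 26.

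The document does not mention a sphericity test, a Greenhouse-Geisser or Huynh-Feldt correction, a multivariate test, a mixed model, the error term for the planned comparisons, a significance level, or the size of each group.

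**The concern.** With three times, the ordinary repeated-measures F holds its level only if the T0–T1, T0–T2 and T1–T2 differences all have the same variance. The design gives little reason to expect that. At T0 the renal values come from patients awaiting a kidney; at T1 and T2 they come from patients with a graft. The three times are also unevenly spaced, which is a milder reason to doubt the assumption for the questionnaires.

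When the assumption fails, the uncorrected F rejects too often under no effect. This one test carries the study's hypotheses on emotional condition, renal function and spending. The planned comparisons have a related problem. An error term pooled over all three times is too small for the more variable differences and too large for the less variable ones.

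**Working it through.** The plan gives no alpha, power or sample-size figure, so there is no design number to reproduce. The participant flow is consistent: 35 − 3 − 1 − 3 = 28, and 28 − 2 = 26.

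**Inputs**
- From the document: N = 26, two groups, three times. Between-subject error df = 26 − 2 = 24; within-subject error df = 2 × 24 = 48.
- Assumed: 5% level, 13 per arm, normal data, equal covariance in both groups, and all SDs and correlations over time.

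**Overall group-by-time test**

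Let λ1 and λ2 be the variances along the two principal within-subject time contrasts. Then ε = (λ1 + λ2)² / [2(λ1² + λ2²)], which lies between 0.5 and 1. With no effect,

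F = [(λ1X1 + λ2X2)/2] / [(λ1W1 + λ2W2)/48],

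where the X are chi-square on 1 df and the W are chi-square on 24 df. The uncorrected test rejects above the 5% point of F(2,48), which is 3.191.

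At ε = 0.5 (λ2 = 0) the statistic is exactly F(1,24), so the ceiling is P(F(1,24) > 3.191) = 8.7%. By simulation over ε:

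| ε | 1 | 0.9 | 0.75 | 0.6 | 0.5 |
|---|---|---|---|---|---|
| Actual size | 5.0% | 5.5% | 6.4% | 7.6% | 8.7% |

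Assumed patterns (correlations in the order T0–T1, T0–T2, T1–T2):

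| Pattern | ε | Actual size |
|---|---|---|
| Equal SDs, 0.7/0.5/0.6 | 0.92 | 5.4% |
| Equal SDs, 0.8/0.4/0.4 | 0.75 | 6.3% |
| SDs 4:3:1, all 0.3 | 0.85 | 5.7% |
| SDs 4:1.5:1, all 0.3 | 0.62 | 7.4% |
| SDs 6:1.5:1, all 0.3 | 0.55 | 8.0% |
| SDs 3:1:1, 0.1/0.1/0.7 | 0.55 | 8.1% |

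The first two rows stand for psychological scores and the other four for renal indices. Worked example for the second row: the two λ are 0.2 and 0.733, so ε = 0.933² / [2(0.04 + 0.538)] = 0.75.

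**Planned comparisons, if the error is pooled**

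Each comparison is read as the group difference in change between two times. Let V be the variance of a time difference. The ratio of the comparison's true variance to the pooled variance is

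r = 3V / (V01 + V02 + V12).

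The three ratios always sum to 3, so they cannot all exceed 1. The pooled test rejects above the 5% point of F(1,48), which is 4.043. When λ2 = 0 its size is P(F(1,24) > 4.043/r).

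- T0 carries all the variance (V01 = V02, V12 = 0): r = 1.5, 1.5 and 0. The T0 comparisons run at P(F(1,24) > 2.695) = 11.4%; T1–T2 runs at about 0%.
- Individual change is linear across the three times (V02 = 4V01 = 4V12): r = 2 for T0–T2, giving P(F(1,24) > 2.021) = 16.8%. For the adjacent pairs r = 0.5, giving P(F(1,24) > 8.085) = 0.9%.
- SDs 3:1:1 as in the table: V01 = V02 = 9.4 and V12 = 0.6, so r = 3 × 9.4/19.4 = 1.45 for the T0 comparisons, which run at 10.6% to 10.7%.
- Mild case, equal SDs with 0.7/0.49/0.7: T0–T2 runs at 9.4% and each adjacent pair at about 3.1%.

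**With the remedy.** Greenhouse-Geisser brought the overall test to 4.5% to 5.1% in every pattern simulated for it. A contrast-specific error on 24 df held each comparison at 4.9% to 5.1%.

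**Sensitivity.** A 10/16 split gives 8.7% overall and 11.5% for the T0 comparisons when T0 carries all the variance. With N = 35 the two ceilings are 8.6% and 16.7%.

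**The case against.** The strongest reply is that this is under-specification and not a demonstrated invalid test. The section names a repeated-measures analysis of variance with Fisher's F. That most naturally means the univariate F, but it does not rule out a correction at the analysis stage. No error term is stated, and with contrast-specific errors the planned comparisons hold their level. This stands, so the second half of the point is conditional.

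The size also depends on covariances that the document does not give. For the questionnaires the inflation may be small: correlations of 0.6/0.5/0.6 give about 5.1%. For renal values the result turns on the T1 spread as much as on T0. With SDs of 4:3:1 the overall size is 5.7%, and nothing shows that T0 dominates for each of the three indices. This also stands, and it is why a range is given. It does not remove the point, because equal difference variances across a transplant would be a coincidence, and under normality with equal group covariances any departure raises the size of the overall test.

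A reader might go further and infer that every planned comparison is inflated to about 11%. The document does not support that: no pooled error is stated, 11% belongs to one pattern and to two of three differences, the ceiling is nearer 17%, and other comparisons become conservative. A reader might also infer material inflation for every continuous outcome, or almost no power for T1 against T2. The first would need a variance structure for each outcome. The second was not calculated, since all figures here are error rates under no effect.

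Finally, testing many outcomes with no stated primary may distort the error rate more than this does. That is a separate matter and bears only on priority.

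**Conclusion.** The point holds as an omission with a modest, bounded effect. As written, the uncorrected group-by-time test has an actual level of about 5.4% to 6.4% under plausible psychological patterns, about 6% to 8% under assumed renal patterns, and never more than 8.7%. The ceiling is a limit, not an expected value. No expenditure pattern was computed, so for that outcome only the ceiling applies.

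Pooled-error planned comparisons, if used, are affected more and in both directions: about 11% when T0 dominates, up to about 17% at worst, and well below 5% for others.

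All of this assumes a 5% level, normality and equal covariance in the two groups. The 26 patients are taken as 13 per arm, although the split matters little. The SDs and correlations are assumptions throughout. Severity: minor to moderate.

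**What to change.** Add to the Statistical analysis section: the significance level; that the group-by-time interaction will be reported with the Greenhouse-Geisser correction for every continuous outcome; and that each planned comparison between groups will use the error variance of its own time difference, on 24 degrees of freedom with 26 patients, and not the pooled within-subject error. The last is equivalent to a two-sample comparison of change between the two times concerned.

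This takes two or three sentences and no new data. The section is written in the future tense, so on its own wording the choice is still open. The price is an overall test at about 4.5% instead of 5% when sphericity holds, and a slightly higher critical value for the comparisons: 4.260 for F(1,24) against 4.043 for F(1,48).

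### Effectiveness is tested on at least 11 outcomes, 10 of them with up to three time contrasts, with no lead outcome, lead time, error control or success rule, so an isolated p just under 0.05 cannot by itself support the claim.

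*Combined protocol and SAP*

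**What the plan says.** The hypothesis at the end of the Background is that expressive writing "produces an improvement in the emotional condition, levels of adherence and renal function, and a decrease in healthcare spending". It sets four domains side by side and ranks none.

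The Statistical analysis section states its purpose as "In order to evaluate the effectiveness of the expressive writing intervention". The method is repeated-measures analysis of variance, and "planned comparisons between the two randomized groups will be performed on psychological variables, the renal function indices and the health expenditure". On time it says: "The times taken into consideration will be T0, T1, T2 and the differences between T0, T1 and T2 will be respectively evaluated". On adherence: "To test the hypotheses on the dichotomous variable of adherence, Chi Square test will carry out". No time is given for that test.

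The measures are listed under Pre-operative phase (T0): BDI, STAI-Y1, STAI-Y2, TAS-20, IRI, HLC, an ad hoc cost questionnaire, the yes/no adherence item ("Have you ever forgotten to take the drugs prescribed by your treatment plan") and renal indices. The renal list is given by example: "pre-transplant renal function values, such as Creatinine, CDK-EPI and azotemia, were collected".

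Material and Method reports the number available: "The final sample is $n = 26".

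Nowhere do the documents name a primary outcome, primary time, significance level or multiplicity adjustment. They do not say whether the planned comparisons depend on a significant group-by-time F, or which results would count as showing effectiveness.

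**The concern.** All these tests serve one stated purpose, and nothing says which of them answers the question. Someone reading the results could not tell a success fixed in advance from one picked out of many. With 26 patients and this many tests, a single result just below 0.05 is an ordinary chance finding even if the intervention does nothing. Reported as evidence of effectiveness, it would carry much less weight than its p-value suggests.

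Calling the comparisons planned does not solve this, because no contrast is ranked above another. Requiring a significant F first would limit error within one outcome but not across ten.

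**Working it through.** **Plan's own figures.** There is no significance level, power or sample-size calculation to reproduce. The patient flow in Material and Method is consistent: 35 − 3 − 1 − 3 = 28, and 28 − 2 = 26.

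**Count of tests.** Six psychological scores + one cost measure + three named renal indices = 10 outcomes under analysis of variance. Adding adherence gives 11. This is a minimum, because the renal list is by example and the plan does not say whether IRI or HLC subscales are scored. The time contrasts are T0-T1, T0-T2 and T1-T2, so there are up to 10 × 3 + 1 = 31 tests.

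**Simple benchmark.** For m independent tests at 5%, the chance of at least one false positive is 1 − 0.95^m.
- m = 11: 43.1%, with 11 × 0.05 = 0.55 false positives expected.
- m = 31: 79.6%, with 1.55 expected. This is too high, because only two of the three time contrasts are free and the outcomes are correlated.

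**Simulation under no effect.** Assumptions, none of them in the documents: two-sided 5% per test, 13 per arm, normal outcomes, correlation 0.5 between times. Each contrast is a t test on the between-arm difference in change. The group-by-time F has 2 and 48 degrees of freedom. There were 20,000 trials per setting. Adherence is left out, so the figures cover the continuous outcomes only.

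Chance of at least one significant result, in either direction:

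| Correlation between outcomes | 10 outcomes, ungated | 10 outcomes, F-gated or T0-T2 only | 8 outcomes, ungated | 8 outcomes, F-gated or T0-T2 only |
|---|---|---|---|---|
| 0 | 73% | 40% | 65% | 33% |
| 0.3 | 67% | 36% | 60% | 30% |
| 0.5 | 57% | 29% | 52% | 26% |
| 0.7 | 45% | 22% | 42% | 20% |
| Clustered | 65% | 34% | 55% | 27% |

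The eight-outcome columns drop IRI and HLC, for which the documents give no direction of benefit. The clustered row assumes 0.6 among BDI, STAI and TAS-20, 0.8 among the renal indices and 0.1 otherwise. At correlation 0.9, the gated or T0-T2 figure falls to about 12-13%. A 10/16 split or a time correlation of 0.8 moves the 0.3 row by about 1 point.

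**Favourable results only.** The hypothesis is directional, so a result favouring control would not be claimed as effectiveness. Counting only results in the intervention's favour at two-sided 5% (nominal 2.5%), with eight outcomes at correlation 0 / 0.3 / 0.5 / 0.7:
- ungated: 42 / 36 / 30 / 24%
- T0-T2 only: 18 / 16 / 13 / 10%

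As a check, eight independent tests give 1 − 0.975^8 = 18.3%, which agrees with the simulated 18%.

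**The case against.** The strongest reply is that the hypothesis joins its four domains with a conjunction. If all four had to improve before effectiveness was claimed, error would not inflate across domains. That is correct, but the documents set no such rule. Even under it, the emotional and renal domains each hold several measures, and nothing says which one decides.

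A second reply is that two-sided any-result rates overstate the risk of a false claim of benefit. This stands, and it is why the favourable-only figures are given. They are roughly half the two-sided ones where only T0-T2 is tested, but still about four to seven times their nominal 2.5% (10/2.5 = 4; 18/2.5 = 7.2).

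A third is that a trial this small is exploratory by nature. The documents never say so; the title and the analysis section both speak of effectiveness. If an exploratory purpose is meant, stating it would meet much of the point.

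A last reply is practical. Material and Method reports recruitment, dropout and the final sample in the past tense, so leads named now may be post hoc. That limits what the fix can achieve and makes disclosure part of it.

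**Conclusion.** The point stands as a gap that should be closed. With any one significant result read as support, and correlations between outcomes of 0 to 0.7, the either-direction false-positive chance is about 42-73% ungated and about 20-40% if F-gated or restricted to T0-T2. The conclusion does not depend on the exact values assumed for significance level, arm sizes and correlations, but the percentages do.

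Three stronger readings go further than the documents allow.
- A reader might infer that error is at least four times nominal on every reading. It is not: one eight-outcome setting gives 19.8%, the rate is lower at higher correlation, and an all-domains rule would behave differently.
- A reader might infer that no positive result could be believed. A very small p-value or a consistent pattern across measures would carry more weight; the limit applies to an isolated p just under 0.05.
- A reader might infer that results have already been selected. The analysis is described in the future tense, and nothing shows that arm-level data have been examined.

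**What to change.** Before arm-level data are examined, or with the post hoc choice disclosed if they have been, add the following to the Statistical analysis section.

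- Name one lead variable at T2 for each hypothesised domain: one emotional scale (BDI, STAI or TAS-20), one renal index, total cost and the adherence item. State the recall period the adherence item refers to; if it cannot be established, keep adherence exploratory.
- Compare the continuous leads between arms adjusting for the T0 value, and apply Holm at two-sided 5% overall across the leads.
- State that a Holm rejection supports a claim for that domain only, and that overall effectiveness across the four domains is claimed only if all leads succeed.
- Report all other scales, indices and time contrasts as exploratory estimates with confidence intervals, and say whether they depend on the group-by-time F.

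A single primary outcome or a fixed hierarchy would also do. Replacing chi-square with Fisher's exact test is a separate, optional change.

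The rule does its job: with four leads (adherence tested by Fisher's test in all 26), simulated familywise error is 3.0-4.1%, against 11.1-16.9% with no adjustment.

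The cost is wording, possibly disclosure, and power. For a 0.8 SD effect at 13 per arm and an assumed T0-T2 correlation of 0.5, the noncentrality is 0.8 / √[(1 − 0.5²) × 2/13] = 2.36 on 23 degrees of freedom. Power is about 62% at 5%. At the strictest Holm step it falls to 43% with three leads (0.05/3 = 0.0167) or 38% with four (0.05/4 = 0.0125). Allowing for chance imbalance at T0, the figures are 60 / 41 / 36%. If T0 says little about T2, as may be so for renal values taken before transplant, power is nearer the unadjusted 50 / 32 / 28%. Power for the all-leads claim cannot exceed that of the weakest lead.

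### On the psychological scales, T0 is only a level of time; with similar SDs at T0 and follow-up, adjusting T1 and T2 for it would usually narrow the arm comparison, by an amount the document does not let us fix

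*Combined protocol and SAP*

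**What the plan says.** The Statistical analysis section of the combined protocol and SAP sets out a repeated-measures ANOVA. It adds that "planned comparisons between the two randomized groups will be performed on psychological variables, the renal function indices and the health expenditure". On the role of time it says "The times taken into consideration will be T0, T1, T2 and the differences between T0, T1 and T2 will be respectively evaluated". No covariate, ANCOVA or other baseline adjustment is mentioned anywhere.

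The design makes T0 a pre-treatment measurement of the same outcomes:

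- Pre-operative phase (T0): "The time of admission, just before the kidney transplant".
- Writing Phase (WP): "Five days after the operation, patients belonging to the experimental group, performed the writing task".
- Discharge (T1) and three-month follow-up (T2): "all participants filled the questionnaire completed before the operation".

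The text does not say outright whether the planned group comparisons are made on change from T0 or on the score at a visit. Its emphasis on differences between times points to change.

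**The concern.** T0 comes before the writing task, so the intervention cannot have affected it, and it is the same instrument as the outcome. It can therefore serve as a predictor of T1 and T2. Entering it as a level of time does not use it that way. A change score in effect fixes the coefficient on T0 at 1. A comparison at a single visit fixes it at 0. ANCOVA estimates it from the data.

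With only 26 patients analysed, a wider interval than the collected data require matters. The stake is precision: how narrow an interval, and how much power, the trial gets for each psychological scale.

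**Working it through.** **Inputs from the document.** Material and Method gives the patient flow: 35 − 3 − 1 − 3 = 28, then 28 − 2 = 26. This reproduces the stated final sample.

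**Inputs not in the document, so assumed.** Arm sizes are 13 and 13 (10 and 16 also checked). Data are normal, with the same covariance in both arms. r is the correlation between T0 and follow-up. k is follow-up SD divided by T0 SD. Follow-up SD is set to 1. Intervals are 95%.

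**Variance factors for the arm difference at one visit.** Each is multiplied by 2/13; √(2/13) = 0.392.

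- Unadjusted visit score: 1, with 24 df.
- Change from T0: 1 + 1/k² − 2r/k, which is 2(1 − r) when k = 1, with 24 df.
- T0-adjusted: (1 − r²) × 23/22, with 23 df. The factor 23/22 = 1.045 pays for estimating the slope at N = 26.

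The critical values are t = 2.064 (24 df) and 2.069 (23 df).

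**Example, r = 0.5, k = 1.** Change: SE = √1 × 0.392 = 0.392, half-width 0.81 SD. Adjusted: SE = √(0.75 × 1.045) × 0.392 = 0.347, half-width 0.72 SD. The ratio is 1.13. For an illustrative 0.8 SD difference at two-sided 0.05, power is about 50% for change and 60% adjusted. At r = 0.7 it is about 71% and 76%.

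**Interval width relative to T0-adjusted** (simulation, 40,000 trials per cell, agreeing with the formulas):

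| r | Change, k = 1 | Change, k = 1.25 | Change, k = 0.75 | Unadjusted visit, any k |
|---|---|---|---|---|
| 0.3 | 1.21 | 1.10 | 1.44 | 1.02 |
| 0.5 | 1.13 | 1.03 | 1.36 | 1.13 |
| 0.7 | 1.06 | 0.99 | 1.31 | 1.37 |
| 0.8 | 1.03 | 0.98 | 1.31 | 1.63 |
| 0.9 | 1.00 | 1.00 | 1.38 | 2.24 |

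At k = 1 the adjusted interval is narrower than the change interval for r below about 0.90, and narrower than the unadjusted one for r above about 0.22. With arms of 10 and 16, r = 0.5 and k = 1, the widths are 1.65 (change and unadjusted) and 1.46 (adjusted), again a ratio of 1.13.

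**Worst case for adjusting.** The change variance can be written (1 − r²) + (1/k − r)², and the unadjusted variance (1 − r²) + r². Neither can fall below 1 − r². So the most that adjustment can cost in width against either visit contrast is √(23/22) × 2.069/2.064 ≈ 1.025, about 2.5%.

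**Other contrasts.**

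- T1-to-T2 difference: with equal correlations, adjustment makes it about 2.4% wider, so there is no gain.
- Group main effect: it averages in the pre-treatment T0 score. For an effect present at both follow-ups, its SE rescaled to that effect is 1.5 × √((1 + 2r)/3) × 0.392 = 0.480 at r = 0.5. The T0-adjusted mean of T1 and T2 has SE 0.284.
- Joint 2-df adjusted test against the 2-df group-by-time F: the direction varies. With a 1 SD effect at both visits, k = 1 and r = 0.5, power is 85% against 73%. With a 0.8 SD effect at T2 only, it is 73% against 79% (k = 1.25, r = 0.7) and 60% against 67% (k = 1.5, r = 0.6).

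**The case against.** The strongest reply is that no error is shown. Repeated-measures ANOVA with planned group comparisons is a valid analysis, and ANCOVA is an alternative to it. That stands. A reader might infer from this point that the planned analysis is biased or invalid; nothing in the document supports that.

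Second, every decisive input is assumed. That also stands, and r = 0.5 with equal SDs flatters adjustment: it is where change and unadjusted comparisons are equally precise, so the gain over the better of the two is at its largest. The uncertainty is lopsided, however. The possible loss in width is capped at about 2.5%, while the possible gain is several times that.

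Third, the largest ratios (1.37 to 2.24) belong to unadjusted visit comparisons, and the weak main-effect results to a test on which the plan never says inference rests. A reader might take those as the expected loss. The text fits change from T0 better, so they are secondary.

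Fourth, a reader might infer that adjustment always wins. It does not. It gains nothing on T1-to-T2, and a joint adjusted test put in place of the F could lose about 6 to 7 power points when the effect is at T2 only and follow-up SDs exceed the T0 SD. It would usually gain when the effect is at both visits and r is about 0.3 to 0.6.

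Fifth, the psychological T0 is pre-transplant too, so surgery could change its SD or correlation with follow-up. That is fair, and it is why the result is conditional on similar SDs. The condition has still less footing for the renal indices, where "in order to assess the pre-transplant renal function values, such as Creatinine, CDK-EPI and azotemia, were collected", and for expenditure, measured by "a questionnaire for the evaluation of healthcare costs, built ad hoc". The point should not be extended to either without checking their SDs and correlations.

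**Conclusion.** The point holds as one of precision on the psychological scales, for consideration rather than as a defect that undermines the trial. With 13 per arm and equal SDs, the change-from-T0 interval is wider than it need be by about a fifth at r = 0.3, falling to nothing at r = 0.9. With follow-up SDs a quarter larger than at T0, the gain is small at r = 0.5 and slightly reversed at 0.7 to 0.8. If unadjusted visit comparisons were meant, there is no loss below r of about 0.22 and a growing one above it.

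Where this trial lies in those ranges cannot be read from the document, so confidence is medium. Nor does the point bear on the patients left out of the analysis ("1 refused to perform the writing task, and finally 3 dropped to T2", among others; 35 − 26 = 9 in all). Adjustment for T0 does not repair that removal, which is a separate issue.

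**What to change.** For each psychological scale, report the arm difference at T1 and at T2 from an ANCOVA adjusted for that scale's T0 score, with 95% confidence intervals. With 26 complete cases, one ANCOVA per visit is enough and a mixed model is not needed. Name one visit as the main comparison, so that two visits do not become two unplanned chances. Keep the planned group-by-time F beside it rather than replacing it, and state that the group main effect does not carry inference. The T1-to-T2 contrast can stay unadjusted.

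The cost is a few sentences in the SAP and one degree of freedom per model, plus the small width penalty shown in the working. T0 is already collected.

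Material and Method already reports the final sample. If outcomes have been seen, label the adjusted analysis as a later change and show the planned ANOVA next to it.

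### The plan does not say which F-test or between-arm contrast supports efficacy, and its T0/T1/T2 differences can be read as within-arm changes that include the effect of the transplant

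*Combined protocol and SAP*

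**What the plan says.** The hypothesis, stated just before Material and Method, is that "the expressive writing treatment produces an improvement in the emotional condition, levels of adherence and renal function, and a decrease in healthcare spending". It does not refer to the control arm.

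The Statistical analysis section gives its purpose as "In order to evaluate the effectiveness of the expressive writing intervention" and says that "an analysis of variance with repeated measures (Fisher's F) and planned comparisons between the two randomized groups will be performed". The outcomes are the psychological variables, the renal indices and health expenditure. The next sentence reads "The times taken into consideration will be T0, T1, T2 and the differences between T0, T1 and T2 will be respectively evaluated". Adherence, a yes/no answer, gets a chi-square test with no time point and no statement of what is compared with what.

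On timing, the T0 assessment takes place at admission, before surgery. Writing begins on the fifth postoperative day, and no assessment is listed between surgery and writing. T1 is discharge and T2 is three months.

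**The concern.** A two-arm, three-time repeated-measures ANOVA produces three F-tests: group, time, and group-by-time. The plan does not say which one answers the hypothesis, and the planned comparisons are not defined (at each time, on change, or within arm).

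The choice matters because of where T0 sits. Every T0-to-T1 and T0-to-T2 change spans the transplant in both arms.

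- The time F-test and any within-arm change measure surgery and writing together.
- The group F-test averages in T0, which no writing can have affected.
- Only a between-arm contrast in change, or a baseline-adjusted comparison after treatment, isolates the effect of writing.

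An improvement seen in the expressive arm but not in the control arm could then be presented as efficacy, although the two arms were never compared directly. Material and Method already reports the final sample while the analysis is still in the future tense, so an unnamed contrast could also be settled late.

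**Working it through.** **Inputs from the document.** 35 recruited; losses of 3, 1 and 3 leave 35 − 3 − 1 − 3 = 28; two acute rejections leave 28 − 2 = 26, which matches the stated final sample. This is a patient-flow count. The document gives no power calculation, alpha, SD or arm sizes.

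**Assumptions.** Two-sided alpha of 0.05; 13 per arm, with 16/10 and 10/16 as a range; a true change shared by both arms of d = 0 to 1.2 SD of the change score; no effect of writing.

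**1. Group main effect.** If writing shifts T1 and T2 equally by δ, the group contrast averages (0 + δ + δ)/3 = 2δ/3. If the shift appears only at T2, it averages (0 + 0 + δ)/3 = δ/3.

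**2. Time main effect.** Simulation of 20,000 trials, 13 per arm, correlation 0.5 between times (assumed), no effect of writing:

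| Shared shift at T1, T2 (SD) | Time F significant | Group-by-time F significant |
|---|---|---|
| 0, 0 | 4.9% | 5.1% |
| 0.3, 0.6 | 76% | 5.0% |
| 0.5, 0.8 | 96% | 5.1% |

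**3. Within-arm tests compared by significance.** Let p be the probability that a paired t-test in one arm shows significant improvement (non-central t, n − 1 degrees of freedom, non-centrality d√n). The arms are independent, so P(expressive significant, control not) = p_E(1 − p_C). For 13/13:

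| d | p per arm | Expressive only |
|---|---|---|
| 0 | 0.025 | 2.4% |
| 0.2 | 0.098 | 8.8% |
| 0.4 | 0.264 | 19.4% |
| 0.6 | 0.512 | 25.0% |
| 0.8 | 0.754 | 18.5% |
| 1.0 | 0.911 | 8.1% |
| 1.2 | 0.977 | 2.2% |

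At d = 0.6: 0.512 × (1 − 0.512) = 0.25. For 16/10 the peak is 0.612 × (1 − 0.396) = 0.37, at d = 0.6. For 10/16 it is 0.353 × (1 − 0.554) = 0.16, at d = 0.56.

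Simulation of 100,000 trials per scenario agrees (24.8% at d = 0.6, 13/13). Only about 9% of the trials showing that pattern also had a significant between-arm difference in change.

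**4. Between-arm contrast.** In the same simulations the two-sample test on change rejected in 4.9% to 5.1% of trials whatever the shared change, that is about 2.5% in the favourable direction. At 13/13 its power is 23% for a difference of 0.5 SD of change, 50% for 0.8 SD and 69% for 1.0 SD; 80% needs about 1.15 SD.

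**5. Adjusting for T0 rather than subtracting it.** With equal variances and correlation r between T0 and T2, the variance of the adjusted comparison relative to the change comparison is (1 − r²)/[2(1 − r)] = (1 + r)/2. At the assumed r = 0.5 this is 0.75. It never exceeds 1, apart from the one degree of freedom spent on the covariate.

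**The case against.** A reader might infer that the plan has no between-arm test of efficacy, or that it intends to declare efficacy when one arm is significant and the other is not. The text does not support either. Effectiveness is expressly assigned to an ANOVA with planned between-group comparisons, and that model can supply the group-by-time test. The sentence on time differences may do no more than name the levels of the repeated factor, and it does not say within each arm. No passage states that significance in one arm alone counts.

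The size of the risk is also conditional. The document gives no outcome data, so how far both arms move is unknown and may differ between renal indices and, say, empathy or locus of control. If the shared change is very large, both arms become significant and the discordant pattern almost disappears (2.2% at 1.2 SD). The equal split is an assumption too.

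All of this stands, and it limits the point to an unspecified contrast. It does not supply the missing specification. The time differences are placed inside the effectiveness analysis, the within-arm reading is open, and two of the three available F-tests are poor or invalid measures of the writing effect in this design.

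**Conclusion.** The point holds as a gap in specification. The plan names a suitable model and between-group comparisons but not the test on which efficacy rests, and it permits within-arm time comparisons that carry the transplant effect. It does not prescribe them.

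If within-arm significance were used, the favourable false pattern would arise in about 2% to 25% of trials per outcome at 13/13 (peak about 16% to 37% across the splits considered), against 2.5% for the between-arm contrast. These rates rest on the assumed alpha, arm sizes and shared change. Only the total of 26 comes from the document. A description of the false-claim rate as uniformly very high would not be supported: it is high only for moderate shared changes, and only under a decision rule that the plan does not state.

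**What to change.** In the Statistical analysis section, state that:

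- For each continuous outcome, the efficacy test is the between-arm difference at T2 adjusted for that outcome's T0 value (ANCOVA), reported with its 95% confidence interval.
- The same adjusted contrast at T1 is secondary.
- Time effects and within-arm changes are descriptive, and no p-value from them is used for efficacy.
- The adherence chi-square compares the two arms at T2.

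Keep the T0 adjustment for every outcome. T0 is pre-transplant for all of them, so that is no reason to treat some differently. A transplant effect common to both arms cancels in the between-arm comparison, and an unadjusted T2 comparison would discard baseline information already collected.

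The cost is a few sentences and one degree of freedom per model, with no new data. T1 moves to a secondary role. The change does not cure the limited power of 26 patients, and the error rate remains per outcome. Because the sample is already reported as final, the amendment should be dated and should say whether outcome data had been examined.
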